 - History of bariatric surgery or planning to undergo bariatric surgery during study duration
 - Clinically significant depression (patients hospitalized for suicidal ideations or suicide attempts within the past 12 months)
 - Any female nursing, planning a pregnancy, known or suspected to be pregnant, or who has a positive pregnancy screen.
- 3. Non-compensated liver disease with any one of the following hematologic, biochemical, and serological criteria on entry into protocol:
 - Hemoglobin < 10 g/dL;
 - White blood cell (WBC) < 3,500 cells/mm³ of blood;
 - Neutrophil count < 1,500 cells/mm³ of blood;
 - Platelets < 130,000 cells/mm³ of blood;
 - Direct bilirubin > 1.0 mg/dL
 - Total bilirubin >3 mg/dL
 - Albumin < 3.2 g/dL
 - International normalized ratio (INR) > 1.4
- 4. Poorly controlled diabetes mellitus (hemoglobin A1c (HbA1c) > 9%)
- 5. Evidence of other chronic liver disease:
 - Biopsy consistent with histological evidence of autoimmune hepatitis
 - Serum hepatitis B surface antigen (HBsAg) positive.
 - Serum hepatitis C antibody (anti-HCV) positive.
 - Iron/total iron binding capacity (TIBC) ratio (transferrin saturation) > 45% with histological evidence of iron overload
 - Alpha-1-antitrypsin (A1AT) phenotype/genotype ZZ or SZ
 - Wilson's disease

3

- 6. Children who are currently enrolled in a clinical trial or who received an investigational study drug within 180 days of screening or liver biopsy.
- 7. Subjects who are not able or willing to comply with the protocol or have any other condition that would impede compliance or hinder completion of the study, in the opinion of the investigator.
- 8. Failure to give informed consent

Outcome measures:

Primary:

Centrally scored and masked assessment of histologic improvement in NAFLD between the baseline liver biopsy and follow-up biopsy after 52 weeks of treatment, where improvement is defined as: (1) decrease in NAS of 2 or more and (2) no worsening of fibrosis.

• Secondary:

- Reduction in serum aminotransferase and gamma-glutamyl transpeptidase.
- Reduction in MRI-determined hepatic fat fraction.
- Changes to markers of oxidation and anti-oxidant status: malondialdehyde, F2 alphaisoprostane, total antioxidant capacity, oxidized LDL
- Changes in fasting insulin and glucose
- Changes in weight, height, BMI, and waist circumference
- Changes in the Peds QL score
- Changes to any symptoms the patient may have experienced

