3.4 Standard treatment recommendations

The use of prescription or non-prescription medicines or herbal remedies or dietary supplements, consumption of alcohol, and management of various co-morbid illnesses will be discussed with the patients. These recommendations have been prepared by the NASH CRN Pediatric Standard of Care Committee and are approved by the NASH CRN Steering Committee to be applied across all study sites. This will help ensure that the patients in both groups receive the same standard of care treatment for NAFLD.

Enhanced Lifestyle Intervention

All children, including those in the placebo group will receive an intervention in the form of standardized lifestyle intervention recommendations consistent with the latest recommendations from the American Academy of Pediatrics (AAP). Assessing the impact of such an intervention on NAFLD will be important. Attaining a healthy weight is the cornerstone of current treatment of pediatric NAFLD, given the lack of proven pharmaceutical therapy in this age group and the strong association of NAFLD with excess adiposity, in particular central adiposity.⁶³ Weight loss has been associated with improvements in liver enzymes and histology in adults with NAFLD, while weight loss in children with NAFLD has been shown to improve serum aminotransferase levels in small pilot studies.^{36,64,65} Therefore, lifestyle intervention through changes in diet and exercise will be encouraged for participants in both the placebo and active study drug treatment group of the CyNCh trial, as this represents the current standard of care for children.

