4.2 Inclusion criteria

Patients must satisfy all of the following criteria to be eligible for enrollment:

- Children age 8-17 years inclusive.
- Liver biopsy within 90 days of screening visit and not more than 120 days before randomization.
- Clinical history consistent with NAFLD.
- Definite NAFLD based upon liver histology.
- No evidence of any other liver disease by clinical history or histological evaluation
- A histological severity of NAFLD Activity Score (NAS) \geq 4.
- Sexually active female participants of childbearing potential (i.e., not surgically sterile [defined as tubal ligation, hysterectomy, or bilateral oophorectomy) must agree to utilize the same two acceptable forms of contraception from screening through completion of the study and to complete a pregnancy test at each study visit. The acceptable forms of contraception for this study include hormonal contraceptives (oral, implant, transdermal patch, or injection) at a stable dose for at least 1 month prior to screening, and barrier (condom with spermicide, diaphragm with spermicide). Sexual activity will be ascertained at each study visit for post-menarchal females and if sexually active, subject must verify use of the same 2 acceptable forms of contraception.
- Participants must be able to swallow cysteamine bitartrate DR capsules.
- Written informed consent from parent or legal guardian.
- Written informed assent from the child.

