6.11 Procedures for unmasking treatment assignment

Treatment assignments are double masked throughout the study until all data collection for the CyNCh trial has been completed (i.e., after completion of the 24 week post trial follow-up for all participants). Every effort will be made to maintain the masking throughout the study except in emergencies. The code of specific pharmacological treatment will not be broken without the knowledge of the clinical center's principal investigator and the study leadership.

Unmasking of study medication may occur under the following conditions:

- Severe allergic reaction (Stevens-Johnson Syndrome): Study medication is stopped indefinitely. The patient, primary care provider (PCP), and the investigator may be unmasked.
- **Pregnancy during the study:** Study medication will be stopped indefinitely, and the coded medication may be unmasked. The patient, PCP, and investigator will be notified of the associated risks of teratogenicity.
- **Development of hepatotoxicity:** Hepatotoxicity will be defined as the development of jaundice with a serum direct bilirubin of > 1.0 mg/dL and an increase in the baseline ALT and AST value that is two-fold or > 400 U/L during treatment. Study medication will be discontinued; however, there will be no unmasking until study conclusion.

The Data and Safety Monitoring Board will review all instances of unmasking that occur.

7. Statistical design and analysis

7.1 Primary hypothesis:

Cysteamine bitartrate DR at 9-12 mg/kg orally daily for 52 weeks is better than placebo in improving liver histologic parameters as measured by the NAFLD activity score in children with NAFLD.

Secondary aims:

- To assess safety and tolerability of cysteamine DR during the 52 week treatment period
- To assess the effect of cysteamine DR on:
 - Serum alanine aminotransferase (ALT), serum aspartate aminotransferase (AST) and serum γ -glutamyl transferase (GGT).
 - Liver fat as measured by MRI.
 - Markers of oxidation and anti-oxidant status: malondialdehyde, F2 alpha-isoprostane, total antioxidant capacity
 - o Insulin resistance
 - Anthropometrics
 - o Quality of Life
 - o Liver related symptoms

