7.2 Outcome measures

Primary outcome measure:

The primary outcome measure, improvement in NAFLD from the start of treatment to the end of treatment at 52 weeks, is defined for each patient as:

- Improvement in NAS score by 2 or more points, and
- No worsening of the fibrosis score

Secondary outcome measures:

- *Conversion from a diagnosis of NASH to not-NASH.* For the subset of patients with NASH at enrollment, determine the proportion whose 52-week liver biopsy results in a centrally determined histological diagnosis of not-NASH
- *Change in NAS*. Change in NAS, is defined for each patient, as the difference in 52 week vs. baseline NAS scores
- *Specific histologic features.* Changes in specific histological scores, defined for each patient, as the difference in 52 weeks vs. baseline, in the following histological features from centrally scores liver biopsies:
 - **o** Fibrosis
 - o Steatosis
 - Lobular inflammation
 - Portal chronic inflammation
 - **o** Ballooning

Change from stage 1b to 1a fibrosis. For the subset of patients with stage 1b fibrosis at baseline, determine the proportion whose 52-week liver biopsy results in a centrally determined histological diagnosis of fibrosis 1a.

• *Serum aminotransferase*. Change in serum aminotransferase, is defined for each patient, as the difference in 52 week vs. baseline serum aminotransferase

- *Gamma-glutamyl transpeptidase*. Change in serum gamma-glutamyl transpeptidase, is defined for each patient, as the difference in 52 week vs. baseline serum gamma-glutamyl transpeptidase
- *MRI-determined hepatic fat fraction*. Change in MRI-determined hepatic fat fraction is defined for each patient, as the difference in 52 week vs. baseline MRI-determined hepatic fat fraction
- *Markers of oxidation and anti-oxidant status*. Change in markers of oxidation and anti-oxidant status, is defined for each patient, as the difference in 52 week vs. baseline values of the following markers:
 - o Malondialdehyde,
 - o F2alpha-isoprostane,
 - o Total antioxidant capacity, and
 - Oxidized LDL
- *Fasting insulin.* Change in fasting insulin, is defined for each patient, as the difference in 52 week vs. baseline fasting insulin
- *Fasting glucose*. Change in fasting glucose, is defined for each patient, as the difference in 52 week vs. baseline fasting glucose
- *Obesity measures.* Change in obesity measures, is defined for each patient, as the difference in 52 week vs. baseline values of the following obesity measures:

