7.3 Statistical analysis

Primary outcome measure:

Statistical analyses for the primary hypothesis will follow the intention-to-treat paradigm, which means that all randomized patients with baseline and 52 week liver biopsies will be included in the treatment group to which they were assigned. Any randomized patient who does not have the requisite biopsies will be accounted for and compared by assigned treatment group.

Since the primary outcome measure, defined in Section 7.2, is a binary indicator of improvement in histologic activity score after 52 weeks of treatment compared to baseline and since the randomization is stratified by clinic, P-values will be derived from the Mantel-Haenszel $\chi 2$ test for stratified 2x2 tables. The proportion of patients improved in the group assigned to cysteamine DR will be compared to the group assigned to placebo and a two-tailed p-value of ≤ 0.05 will be considered statistically significant.

Secondary outcome measures:

Statistical analyses for the secondary measures that are continuous measures or scores will be carried out using separate bootstrapped mixed-effects-models corresponding to each individual change measure (defined in Section 7.2) as the response variable, with random effects for variation by clinic, and an indicator variable for comparing cysteamine DR (compared to placebo). The regression coefficient estimate for the indicator variable is the treatment effect for each secondary measure and is interpreted as the mean of the per-patient differences in each secondary outcome measure in the cysteamine DR group minus the corresponding mean differences in the placebo group. Statistical significance for each secondary treatment effect will be achieved if zero is not included in the nominal 95% bootstrapped confidence limits for each secondary measure. Bootstrapping with 2,000 replications will be performed to achieve 95% confidence limits that account for, in advance,

potential non-normality in the continuous secondary outcomes measures or scores. The bootstrapping estimation will be carried out using Stata software.

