10.3 Blood collection schedule (amounts in mL)

Complete blood count: Hemoglobin, hematocrit, mean corpuscular volume (MCV), white blood cell count (WBC), white blood cell differential, platelet count

Comprehensive metabolic panel: calcium, carbon dioxide, chloride, glucose, potassium, sodium, creatinine, blood urea nitrogen (BUN), uric acid

Hepatic panel: Total bilirubin, direct bilirubin, aspartate aminotransferase (AST), alanine aminotransferase (ALT), alkaline phosphatase, gamma glutamyltransferase (GGT), albumin, total protein, prothrombin time (PT), international normalized ratio (INR)

Lipid profile: triglycerides, total cholesterol, LDL and HDL

Etiologic tests: Hepatitis B surface antigen (HBsAg), hepatitis C antibody (anti-HCV), alpha-1antitrypsin level, ceruloplasmin. Autoantibodies: (ANA, AMA, ASMA), serum iron, ferritin, and total iron binding capacity (TIBC) Glossary

10.4

A1AT	alpha-1-antitrypsin
ALT	alanine aminotransferase
AMA	antimitochondrial antibody
ANA	anti-nuclear antibody
anti-HCV	hepatitis C antibody
ASMA	anti-smooth muscle antibody
AST	aspartate aminotransferase
AUDIT	Alcohol Use Disorders Identification Test
BMI	body mass index (kg/m ²)
BUN	blood urea nitrogen
CC	Clinical Center
CRN	Clinical Research Network
DCC	Data Coordinating Center
DDC	Drug Distribution Center
DSMB	Data and Safety Monitoring Board
EMT	epithelial-mesenchymal transition
GCRC	General Clinical Research Center
GGT	gamma glutamyltransferase
HbA1c	hemoglobin A1c
HBc	hepatitis B core antigen
HBsAg	hepatitis B surface antigen
HCC	Hepatocellular carcinoma
HCV	hepatitis C virus
HIPAA	Health Insurance Portability and Accountability Act
INR	international normalized ratio
IRB	institutional review board
MCV	mean corpuscular volume
MRI	magnetic resonance imaging
MRS	magnetic resonance spectroscopy
NIH	National Institutes of Health
NAFL	nonalcoholic fatty liver
NAFLD	nonalcoholic fatty liver disease
NAS	nonalcoholic fatty liver disease activity score
NASH	nonalcoholic steatohepatitis
NSAIDs	nonsteroidal anti- inflammatory drugs
PPARγ	peroxisome proliferator-activated receptor-gamma
PT	prothrombin time
ROS	reactive oxidative species
SAE	serious adverse event
SOC	standard of care
TIBC	total iron binding capacity
WBC	white blood cell count

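### Raw 52-week changes in weight, height, BMI and waist in children aged 8–17 mix growth with adiposity: the between-arm contrast is unbiased, but it loses precision and is hard to interpret

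*Protocol*

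**What the plan says.** The Design Synopsis lists among the secondary outcomes "Changes in weight, height, BMI, and waist circumference". Section 7.2 turns this list into per-patient variables under the label *obesity measures*: "Change in obesity measures, is defined for each patient, as the difference in 52 week vs. baseline values of the following obesity measures". All four are plain differences in kg, cm or kg/m², and the glossary gives BMI in kg/m². No z-score, percentile or other growth standard appears anywhere in the protocol.

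The population in section 4.2 is "Children age 8-17 years inclusive".

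Section 7.3 analyses each continuous secondary outcome in its own bootstrapped mixed model, with random effects for clinic and an indicator for treatment. It names no age, sex, pubertal or baseline term. The treatment effect is the mean per-patient change "in the cysteamine DR group minus the corresponding mean differences in the placebo group". Section 3.2 stratifies randomization by clinic and three bands of baseline body weight, not by age or sex.

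On why weight matters here, section 3.4 says "Attaining a healthy weight is the cornerstone of current treatment of pediatric NAFLD", and both arms receive the same lifestyle recommendations.

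**The concern.** A child of 9 or 13 normally gains height, weight and often BMI over a year, while a 17-year-old may gain little. A raw gain in kilograms therefore does not by itself mean that obesity has worsened, and a small raw loss can understate an improvement. A gain in height says nothing about adiposity. Under section 7.3, however, an interval for height that excluded zero would count as a significant effect on one of the *obesity measures*.

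What is at stake is how these secondary results can be read and how precise they are. Section 3.4 also says that it will be important to assess the effect of the lifestyle intervention on NAFLD. Every child gets that intervention, so no randomized contrast exists for it. Anyone who looks at it will have to use changes within patients or within an arm, which is where raw change misleads most.

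**Working it through.** **The plan's own figures.** The protocol gives no SD, effect size or power for the anthropometric outcomes, so there is nothing to reproduce. All growth and SD values below are assumptions, shown as ranges. The design inputs come from section 7.5: 80 per arm, 10% without a 52-week biopsy. Applying that 10% to these outcomes leaves 72 per arm.

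**Step 1. Does growth enter the raw change?** For a child who grows from height h to h + d at constant BMI, weight gain = BMI × ((h + d)² − h²).
- Height 1.40 m, BMI 28, growth 3 cm: 28 × (1.43² − 1.40²) = 2.4 kg.
- Height 1.65 m, BMI 33, growth 8 cm: 33 × (1.73² − 1.65²) = 8.9 kg.

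Section 7.2 would record 2.4 to 8.9 kg as change in an obesity measure although BMI has not moved.

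**Step 2. Is a unit the same across the age range?** One kilogram is 1/1.40² = 0.51 kg/m² at 1.40 m, but 1/1.65² = 0.37 kg/m² at 1.65 m.

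**Step 3. Is the between-arm contrast biased?** Simulation of BMI change, 72 per arm, 20,000 runs per setting. Assumptions: mean growth +0.6 kg/m² with the same distribution in both arms, residual SD 1.5, between-child growth SD 0.2, 0.5 or 1.0.

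| True effect (kg/m²) | Growth SD | Mean raw contrast | Rejection rate, raw | Rejection rate, growth removed | Mean raw change, treated arm |
|---|---|---|---|---|---|
| 0 | 0.2 | −0.002 | 5.1% | 5.2% | +0.6 |
| 0 | 0.5 | 0.001 | 4.9% | 5.0% | +0.6 |
| 0 | 1.0 | 0.002 | 4.7% | 4.9% | +0.6 |
| −1.0 | 0.2 | −0.999 | 97.6% | 97.8% | −0.4 |
| −1.0 | 0.5 | −0.999 | 96.5% | 97.8% | −0.4 |
| −1.0 | 1.0 | −0.998 | 91.2% | 97.6% | −0.4 |

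The contrast recovers the true effect and type I error holds. The change within the treated arm does not recover it: a true effect of −1.0 appears as 0.6 − 1.0 = −0.4.

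**Step 4. How much precision is lost?** For weight, variance ratio = 1 + (growth SD)² / (residual SD)², and interval width ratio is its square root.

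| Growth SD (kg) | Residual SD (kg) | Variance ratio | Width ratio |
|---|---|---|---|
| 1 | 6 | 1.03 | 1.01 |
| 1 | 4 | 1.06 | 1.03 |
| 2 | 6 | 1.11 | 1.05 |
| 2 | 4 | 1.25 | 1.12 |
| 3 | 6 | 1.25 | 1.12 |
| 3 | 4 | 1.56 | 1.25 |

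As a share of total variance, growth runs from 1/37 = 3% to 9/25 = 36%. Steps 3 and 4 compare raw change with growth removed completely. Age and sex predict growth only in part, so these gains are upper limits for the SDs assumed.

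**The case against.** The strongest reply is that section 7.3 plans no test within an arm. Its treatment effect is a difference between randomized, masked, concurrent groups, so expected growth cancels. This stands in full. A reader might infer that growth biases the treatment effect, or that these outcomes cannot show whether the drug changed adiposity. The documents do not support either reading, and step 3 shows why. A chance imbalance in age or sex can shift a single result, but the confidence interval allows for that.

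A reader might also infer that the trial cannot tell whether a histological benefit is independent of weight loss. That is a mediation question, and the protocol neither poses it nor plans an analysis for it. Lifestyle advice is common to both arms, so randomization already deals with it in the primary comparison.

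Three further replies stand in part:
- The loss of precision is mostly modest, and growth does not dominate the variance under any assumption used here.
- Only section 7.2 applies the obesity label. The synopsis simply lists the measures, and sections 1, 3.6 and 7.1 speak of anthropometrics, where height belongs.
- A statistical analysis plan, not shown, could add standardised BMI without contradicting 7.2. But 7.2 states the definition and 7.3 states the model, so this is a choice the protocol has made and not a detail it left open.

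**Conclusion.** The point holds as a weakness of definition and precision in secondary outcomes, not as a bias. The raw changes are valid for comparing arms, provided that expected growth does not differ between them, as randomization ensures unless the drug itself alters growth. They are poor measures of change in adiposity within an arm or across ages 8 to 17. Under the assumed SDs, intervals for weight change are about 1.01 to 1.25 times wider than they would be with growth removed. In the BMI simulation, power for a 1.0 kg/m² effect falls by less than 2 percentage points at the two smaller growth SDs and by about 6 points at the largest. Height is mislabelled in section 7.2. The primary histological outcome, its power and its type I error are unaffected. This is a worthwhile improvement at almost no cost, not a flaw that threatens the trial's conclusion.

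**What to change.** In section 7.2, make change in age- and sex-standardised BMI the BMI outcome: the z-score, or percent of the 95th percentile where obesity is severe. Add waist-to-height ratio, and keep the raw changes in weight, BMI and waist as descriptive results. Take height out of the *obesity measures* and report it, standardised for age and sex, as a growth and safety measure.

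The minimum alternative is to keep the raw outcomes and add age and sex as covariates to the section 7.3 model for them. That recovers much of the available precision, but it does not make within-arm changes readable.

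No data collection changes. Sections 5.2 and 5.4 already record height, weight and waist at screening and at every follow-up visit, and age and sex are known. The cost is a few derived variables and the choice of a growth reference, which should be named before unmasking.

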7.3 Statistical analysis

Primary outcome measure:

Statistical analyses for the primary hypothesis will follow the intention-to-treat paradigm, which means that all randomized patients with baseline and 52 week liver biopsies will be included in the treatment group to which they were assigned. Any randomized patient who does not have the requisite biopsies will be accounted for and compared by assigned treatment group.

Since the primary outcome measure, defined in Section 7.2, is a binary indicator of improvement in histologic activity score after 52 weeks of treatment compared to baseline and since the randomization is stratified by clinic, P-values will be derived from the Mantel-Haenszel $\chi 2$ test for stratified 2x2 tables. The proportion of patients improved in the group assigned to cysteamine DR will be compared to the group assigned to placebo and a two-tailed p-value of ≤ 0.05 will be considered statistically significant.

Secondary outcome measures:

Statistical analyses for the secondary measures that are continuous measures or scores will be carried out using separate bootstrapped mixed-effects-models corresponding to each individual change measure (defined in Section 7.2) as the response variable, with random effects for variation by clinic, and an indicator variable for comparing cysteamine DR (compared to placebo). The regression coefficient estimate for the indicator variable is the treatment effect for each secondary measure and is interpreted as the mean of the per-patient differences in each secondary outcome measure in the cysteamine DR group minus the corresponding mean differences in the placebo group. Statistical significance for each secondary treatment effect will be achieved if zero is not included in the nominal 95% bootstrapped confidence limits for each secondary measure. Bootstrapping with 2,000 replications will be performed to achieve 95% confidence limits that account for, in advance,

potential non-normality in the continuous secondary outcomes measures or scores. The bootstrapping estimation will be carried out using Stata software.

Statistical analyses for each of the secondary measures that are events (binary responses) will be carried out using the same method as for the analysis of the primary outcome measure. Events rates (proportions) in the cysteamine DR group and in the placebo group will be determined and a stratified (by clinic) Mantel-Haenszel analysis for stratified 2x2 tables will the used to obtain a weighted odds ratio as the treatment effect (OR > 1 favors cysteamine DR) and P-value for the significance of the odds ratio estimate; a nominal two-tailed p-value of ≤ 0.05 will be considered statistically significant.

We plan to use nominal P-values when reporting the statistical significance of each secondary outcome, since we have declared such outcomes in advance in hypothesis-driven discussions among the investigators. We will also determine Bonferroni-corrected 95% confidence intervals and P-values for comparison with nominal P-values.

